### **3.2. SPECIFIC AIMS**

#### **3.1.3. Primary Specific Aim**

To evaluate the effect of continuing treatment with caffeine citrate in the hospital on number of days of hospitalization from randomization to discharge up to 48 wks PMA, with censoring at time of transfer or death.

#### **3.1.4. Secondary Specific Aims**

- a. To evaluate the effect of continuing treatment with caffeine citrate in the hospital on number of days to reach physiologic maturity from randomization to discharge up to 48 wks PMA.

- b. To evaluate the effect of treatment with caffeine until 28 days after hospital discharge on all-cause readmissions to a hospital (including apneic and/or apparent life-threatening events) within the first 8 weeks after discharge by 48 wks PMA.
- c. To evaluate the effect of treatment with caffeine until 28 days after hospital discharge on the number of all-cause sick visits to urgent care, emergency rooms, or health care provider's office (including apneic and/or apparent life-threatening events) within the first 8 weeks after discharge by 48 weeks PMA.
- d. To evaluate the side effects and adverse events of caffeine continuation in the hospital and after discharge up to 4 weeks post study drug administration.
- e. To assess the hypothetical cost-savings by the reduction in number of days of hospitalization as a financial benefit of the trial's interventions.

### 3.3. BACKGROUND

AoP is a common diagnosis in moderately preterm infants, most exhibiting clinical signs of AoP as defined by the American Academy of Pediatrics [cessation of breathing for  $\geq 20$  seconds or  $< 20$  seconds if accompanied by bradycardia and/or cyanosis in infants  $<37$  weeks gestational age (GA)]. Moderately preterm infants comprise

one fourth of NICU admissions. In a retrospective cohort study of moderately preterm infants, 92% (23/25) were diagnosed with AoP at 30 weeks post-menstrual age (PMA). Even at 33 weeks PMA, 48% (59/122) of infants had AoP, and apnea may persist beyond 37 weeks, even until  $\sim 44$  weeks PMA. PMA at the time of resolution of apnea is inversely proportional to the GA at birth.

Although respiratory maturation occurs with increased PMA, there is uncertainty regarding the range of PMA at which there is complete resolution of AoP. This uncertainty can delay discharge, as sufficiently mature respiratory control is one of the essential

[figure not shown]

Figure 1. Lorch SA, Srinivasan L, Escobar GJ. Epidemiology of apnea and bradycardia resolution in premature infants. Pediatrics 2011;128:e366-73

physiologic competencies before discharge of the infant as recommended by the American Academy of Pediatrics.

There is wide variability in practice among physicians regarding the timing of discharge. In a retrospective study of discharge timing that included 435 infants born at 30 to 34 6/7 weeks GA and admitted to one of 15 neonatal intensive care units, Eichenwald et al. noted that PMA at discharge ranged from  $35.2 \pm 0.5$  weeks to  $36.5 \pm 1.2$  weeks among the units despite similar criteria for discharge including full oral feeds, resolution of apneic episodes, and ability for thermoregulation. In a large observational study, it was shown that even after infants had fulfilled other criteria for discharge, 15.8% (222/1403) of infants at 34 weeks' PMA had recurrent apneic episodes. Although apneic episodes decrease even without treatment with caffeine, many infants continue to have apneas many days (observation day on Figure 1) after they are ready for discharge. An intervention such as caffeine therapy that can decrease apneic episodes can potentially shorten the hospitalization of infants who are prone to apnea but otherwise ready for discharge. In a retrospective study of 164 infants, 41 (25%) were discharged with caffeine citrate continued at home. The authors did not report any deaths or adverse events. In addition, home caffeine therapy may reduce the number of apneic episodes at home, some of which can lead to readmission to the hospital or sick visits to the emergency room, urgent care, or health care provider.

For many years, methylxanthines, primarily caffeine citrate, have been used to treat AoP. Caffeine acts by inhibiting two of four adenosine receptors stimulating the infant to breathe and reducing apneic episodes. Furthermore, methylxanthines improve function of the respiratory musculature, including increased diaphragmatic contractions. In multiple trials, methylxanthines have been shown to reduce AoP. Caffeine decreases obstructive, central, and mixed apnea. A recent Cochrane review of five randomized controlled trials that included a total of 192 preterm infants indicated that methylxanthine treatment for apnea resulted in less treatment failures compared to placebo [RR 0.44 (95%CI 0.32 to 0.60), NNT 3 (95%CI 2 to 4)] as well as a decreased use of intermittent positive pressure ventilation [RR 0.34 (95% CI 0.12 to 0.97), NNT 13 (95% CI 6 to 100)]. Tachycardia was the only side effect that was more common in the caffeine group. A double-blind placebo-controlled trial showed that weight gain did not differ between intervention and placebo groups. In addition, a large randomized placebo-controlled trial of prolonged treatment with caffeine in extremely preterm infants showed short and long-term benefits of caffeine without evidence of side effects.

Three retrospective cohort studies of caffeine treatment at home for infants at risk for apnea and infants with apnea of infancy have been reported. The median PMA at last dose of caffeine was 34.4 weeks in a large clinical trial while in another large multicenter study, the average PMA at discharge was 35.7 weeks (encompassing infants born at 30 to 33 weeks GA). This illustrates many infants continue to receive treatment late in their hospital course. As apnea can still occur past these PMAs, continuing caffeine beyond the usual duration of treatment through hospital discharge may decrease late episodes of apnea that occur in the hospital. Often, these late apneas can prolong hospital stay due to an additional period of monitoring for further apnea. In addition, continuation of caffeine beyond hospital discharge may prevent complications from AoP that lead to hospital readmission or unplanned healthcare visits. A trial investigating the use of prolonged caffeine citrate treatment would provide high level of evidence and generalizability

to determine the effects on length of hospitalization, readmissions, and sick visits in moderately preterm infants. The proposed trial will evaluate infants for eight weeks following discharge, since infants would have reached at least a PMA of 40 to 44 weeks at the end of the evaluation period. Thus, the number of events of apnea and bradycardia should not differ when compared to full term infants of the same PMA. This is the reasoning for the eight week evaluation period following hospital discharge.

### 3.4. Justification for the Study

Moderately preterm infants represent a relatively large group of neonates who require admission to the NICU, but discharge can be delayed by AoP or other factors. According to the American Academy of Pediatrics guidelines for hospital discharge of preterm infants, infants must have sufficient respiratory control before discharge, yet half of preterm infants were found in one study to continue to have apneic episodes at 33 weeks PMA. According to a study by Eichenwald et al. apnea was one of the two most common factors responsible for prolonging hospitalization. Historically, there has been a fear of discharging preterm infants home too early, as they are at increased risk for continued AoP at home and potentially may experience an apparent life-threatening event requiring an emergency room visit and readmission related to apneic and bradycardic events after discharge. Caffeine treatment is effective in decreasing the episodes of apnea. The current practice is to discontinue its use before discharge and evaluate for development of apneic episodes but this trial could change this paradigm and shorten hospitalization in a safe way by continuing caffeine treatment beyond discharge home.

Apneic episodes frequently recur after discontinuation of caffeine treatment. Hypothetically, continuation of caffeine after resolution of apneas would prevent further apneas and allow for earlier discharge from the NICU, if other competencies of physiologic maturity have been achieved, including temperature regulation and feeding tolerance. Complete maturation of the respiratory center does not occur until as late as 44 weeks in preterm infants. As the average age of discharge of moderately preterm infants is between 35 to 37 weeks, apnea may still occur after discharge. Home therapy with caffeine can potentially decrease re-admissions to the hospital or sick visits due to AoP. To test these hypotheses, a randomized placebo-controlled trial of caffeine is proposed. The aim of this trial is to determine if continuing treatment with caffeine citrate in the hospital in moderately preterm infants with resolved apnea of prematurity instead of discontinuation of treatment in the hospital decreases hospital days. We will also determine if continuing caffeine at home decreases apneic episodes that may occur after discharge. The results of the trial could potentially transform how AoP is managed in moderately preterm infants during hospitalization as well as following discharge.

A trial of continuing and discharging infants on home caffeine therapy is novel, but in several small retrospective reviews and a multicenter observational study, a minority of the infants were discharged on methylxanthine treatment. However, there are no data on the effectiveness and safety of late hospital and home methylxanthine treatment. The proposed trial will be the first of its kind and will help determine if this management strategy is beneficial and safe.

To be able to carry out this multicenter trial, there is need to enroll a large number of moderately preterm infants. Approximately 3000 preterm infants of this gestational age group are admitted a year to the NRN NICUs, with approximately one-third receiving caffeine treatment. Given the vast experience of the study-site principal investigators in multicenter trials as well as the research infrastructure, with research nurses and pharmacists, we believe that the NRN is particularly suitable to successfully perform this multicenter trial.

Potential challenges in performing this trial include:

- a. The administration of study medication at home by the parents without frequent missed doses
- b. Loss to follow up
- c. Inaccurate or missing information regarding re-admission to the hospital or to sick visits
- d. Inaccurate data collection on follow-up forms provided by the parents
- e. Side effects from the study medication

The trial will be approved by each institutional review board (IRB). Parental consent will be obtained for each infant enrolled. Safety is of upmost importance and will be monitored by the Data Safety Monitoring Committee (DSMC) when 25%, 50%, and 75% of the subjects complete the eight-week follow up period (or are lost to follow up). The trial will record side effects and adverse events will be reported to the DSMC periodically. Expedited serious adverse events will be reported per local IRB guidelines and to the NICHD and NRN Data Coordinating Center at RTI.

## SECTION 4. STUDY DESIGN

---

### 4.1. PRIMARY OUTCOME

The primary outcome of the study will be the number of days of hospitalization from randomization to discharge up to 48 weeks PMA, with censoring at time of transfer or death.

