### Exclusion Criteria

- a. On respiratory therapy (oxygen more than room air equivalent for high altitude sites, nasal cannula, continuous positive pressure ventilation, and/or mechanical ventilation).
- b. Infants who would otherwise be discharged home on apnea monitor due to underlying disease or family history, including history of a sibling with sudden infant death syndrome
- c. Parental request for apnea monitor
- d. Congenital heart disease other than atrial septal defect, ventricular septal defect, or patent ductus arteriosus

- e. Neuromuscular conditions affecting respiration
- f. Major congenital malformation and/or genetic disorder
- g. Plans to transfer to a non-NRN site before discharge
- h. Unable to obtain parental or guardian consent

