### **5.2.3. In-hospital Procedures**

Study subjects are infants in the NICU at one of the principal or associated sites of the NRN. Once the attending physician has discontinued caffeine therapy, the infant will be randomized as described in section 5.2.2. The research pharmacist will be notified of enrollment and the infant will receive a once-a-day dose of caffeine citrate at 10 mg/kg/dose (5 mg/kg caffeine base) as part of the treatment group or receive placebo at the same volume and time every 24 hrs and not given less than 12 hours apart. The doses will be weight adjusted on a weekly basis. If the infant is later put NPO, the oral caffeine citrate or placebo will be held until feeding resumes and at the discretion of the attending neonatologist.

In-hospital apnea and bradycardia events will be monitored using individual study site monitor devices. There are no universal definitions for apnea and bradycardia and therefore, diagnoses of these will be left at the discretion of each hospital group of neonatologists (pre-specified) and the neonatal team caring for the infant. The data on apnea and bradycardia will be used to determine physiologic maturity and for the local decision about discharging the babies home. The definitions of apnea and bradycardia will be decided locally. However, for the purposes of this study, significant apnea/bradycardia will be defined as apnea/bradycardia events receiving treatment. Treatment is defined as ordered by the attending physician (e.g. re-starting caffeine, not just stimulation for example). Using local definitions will increase generalizability and interfere less with local decision making.

Data will be collected from the infant's electronic or physical chart. The number of infants who receive CPAP, mechanical ventilation, and/or open label caffeine, other methylxanthine or doxapram for the treatment of apnea/bradycardia after randomization will be noted for the study.

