### 6.2. STATISTICAL ANALYSIS PLAN

The primary analysis will compare number of days of hospitalization from randomization to discharge, death, transfer or 48 weeks PMA, whichever occurs first between the intervention and control groups using median regression controlling for study center and GA group (the two stratification factors for this trial). Likewise, the treatment effect for the secondary outcomes (number of days to physiologic maturity after randomization, number of readmissions and number of sick visits) will be compared using either median regression or a Poisson regression model controlling for study center and GA group.

Secondary analyses will evaluate whether other models better fit the distributions for these outcomes (for example, survival analysis models for the primary outcome and negative binomial or log linear models for the secondary outcomes).

We will examine treatment heterogeneity for the primary outcome by adding interaction terms between treatment and study center, as well as treatment and GA group. If any of these interaction terms are close to statistical significance ( $p<0.1$ ), for treatment heterogeneity by study center, we will attempt to identify centers where the treatment effect may be different (although the statistical power available to conduct such analyses will be fairly limited). If there is

indication of treatment heterogeneity by GA group, we will conduct stratified analyses by GA group to quantify the treatment effect separately by GA group.

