#### 4.7 Database Lock

The database will be locked after all enrolled infants have completed their post-discharge follow-up, died or transferred, or reached 48 wks PMA. Randomization assignment will not be unmasked until after database lock is finalized. Data cleaning and edit check may continue after the database lock and final versions of the analysis files will be archived.

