## 9.2 Efficacy Variables

Primary and secondary efficacy variables are described in the table below.

| Variable                               | Type  | Definition   |  |
|--|-------|--|--|
| Primary Outcome                        |       |  |  |
| Number of days of hospitalization      | Count | The number of days between randomization and hospital discharge. This outcome is censored at 48 weeks PMA and at time of transfer or death   |  |
| Secondary Outcomes                     |       |  |  |
| Number of days to physiologic maturity | Count | Physiologic maturity is defined:  i. Temperature: out of the incubator for at least 48 hours with normal body temperature  ii. Feeding: oral feeding at a volume of at least 140 ml/kg for 48 hours or growing on less than 140 ml/kg/day for at least 48 hours  iii. Respiratory: apnea-free for at least 5 consecutive days  This outcome is censored at 48 weeks PMA. |  |

| Variable  | Type       | Definition  |
|---|------------|---|
| Number of days to physiologic maturity - Temperature                        | Count      | Physiologic maturity is defined:  i. Temperature: out of the incubator for at least 48 hours with normal body temperature  This outcome is censored at 48 weeks PMA.  |
| Number of days to
physiologic maturity –
Feeding                      | Count      | Physiologic maturity is defined:  i. Feeding: oral feeding at a volume of at least 140 ml/kg for 48 hours or growing on less than 140 ml/kg/day for at least 48 hours  This outcome is censored at 48 weeks PMA.            |
| Number of days to
physiologic maturity -
Respiratory                  | Count      | Physiologic maturity is defined:  i. Respiratory: apnea-free for at least 5 consecutive days This outcome is censored at 48 weeks PMA.  |
| Post-menstrual age at discharge   | Continuous | The post-menstrual age of the infant at discharge censored at 48 weeks PMA and at time of transfer or death   |
| Number of all-cause
readmissions within first 4
weeks post-discharge  | Count      | Number of hospital readmissions including apneic events and apparent life-threatening events during first 4 weeks following hospital discharge. The outcome is censored at 48 weeks PMA.                                    |

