## 9.3 Primary Analysis Methods

For the primary analysis, the number of days of hospitalization between randomization and discharge will be compared between the caffeine citrate and placebo groups using either median or robust Poisson regression models. The model will include a fixed effect for treatment group. The model will also be adjusted for the design effect of stratification by site and gestational age. Estimates, p-values and 95% confidence intervals will be presented for treatment group comparisons. In an intent-to-treat fashion, all data will be included in the primary model based on their randomized treatment, regardless of the treatment administered to the patient. If there are important baseline characteristics that differ between randomized treatment groups by chance, additional sensitivity analyses may be conducted to evaluate the impact of those imbalances.

We will examine treatment heterogeneity for the primary outcome by adding interaction terms between treatment and study center, as well as treatment and gestational age group, and following NIH guidelines, treatment and sex. If any of these interaction terms are close to statistical significance (p<0.1), for treatment heterogeneity by study center, we will attempt to identify centers where the treatment effect may be different (although the statistical power available to conduct such analyses will be fairly limited). If there is indication of treatment heterogeneity by GA group and/or sex, we will conduct stratified analyses by GA group and/or sex to quantify the treatment effect separately by GA group/sex.

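### The primary outcome stops at an undefined transfer, so an infant who moves to another network hospital stops contributing hospital days while still hospitalized, and the transfer day is analysed as a completed stay

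*Protocol*

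**What the plan says.** Protocol 4.1 defines the outcome as the "number of days of hospitalization from randomization to discharge up to 48 weeks PMA, with censoring at time of transfer or death". SAP 9.2 has the same rule: "This outcome is censored at 48 weeks PMA and at time of transfer or death". Neither document says what counts as a transfer.

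Eligibility does separate two kinds. The only transfer exclusion is "Plans to transfer to a non-NRN site before discharge" (protocol Section 1, repeated in 5.1.2 and in the SAP). An infant due to move to another network hospital can therefore be enrolled. Protocol 5.2.3 places subjects at "one of the principal or associated sites of the NRN", so the network reaches beyond its principal centers.

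For the analysis, protocol 6.2 compares the "number of days of hospitalization from randomization to discharge, death, transfer or 48 weeks PMA, whichever occurs first", "using median regression controlling for study center and GA group". SAP 9.3 makes the comparison "using either median or robust Poisson regression models". Neither names a method for censored values. Survival models appear only as possible secondary analyses (protocol 6.2, SAP 9.4).

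SAP 4.7 locks the database once infants have "completed their post-discharge follow-up, died or transferred, or reached 48 wks PMA", so transfer is an end state. No section provides for collecting a discharge date after a transfer. SAP 7.3 expects no missing length-of-stay data.

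**The concern.** The endpoint measures time in hospital, and a transferred infant is still in hospital. The plan distinguishes network from non-network moves at entry but drops the distinction at the endpoint. Three things follow:

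- **Incomplete stays enter as complete ones.** The definition speaks of censoring, but the model named for it is ordinary regression on time to the first of four events. A transfer on day 6 is entered as a 6-day stay.
- **Longer stays are cut more often**, because they offer more days on which a transfer can happen. With similar transfer risk in both arms, this trims the longer-staying arm more.
- **Post-discharge outcomes lose these infants.** Readmissions and sick visits are counted from discharge, and a transferred infant has no recorded discharge from which to count.

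The minimum sample size of 878 gives 80% power for a 2-day difference, so there is little room for dilution.

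**Working it through.** **1. The plan's own figure.** The documents give no SD for length of stay, so 878 cannot be derived from their inputs alone. Solving backwards: 439 × 0.95 = 417.05 per arm, and SD = 2 × √(417.05/2) / (1.960 + 0.842) = 10.31 days. The 1174 row gives 10.30, so the two rows agree. The sample size is not in dispute; this only supplies a plausible spread.

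**2. Why counting to transfer shortens the median.** If stay T has survival function S(t) and transfer has a constant daily hazard h, the time to the first of the two has survival S(t) × exp(−ht). The observed median m solves S(m) × exp(−hm) = 0.5.

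Example: lognormal stays, medians 14 and 12, log-scale SD 0.574 (this gives SD 10.3 at median 14), h = 0.00314, so that 5% of placebo infants are transferred.
- Placebo, m = 13.576: S = 1 − Φ(ln(13.576/14)/0.574) = 0.521; exp(−0.0426) = 0.958; product 0.50.
- Caffeine, m = 11.694: S = 0.518; exp(−0.0367) = 0.964; product 0.50.
- Difference: 13.576 − 11.694 = 1.88 days instead of 2.0.

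In this example 2.1% of the shortest quarter of placebo stays are cut, against 9.1% of the longest quarter. Mean placebo days fall by 3.5%, which matters if the robust Poisson option is used.

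**3. Range of sizes.** The transfer rates and the distribution are assumptions. Stays are gamma with medians 14 and 12 and placebo SD 8.2 to 10. The true difference is 2.0 days.

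| Transfer pattern | Transferred, placebo arm | Transfer day taken as end of stay | Kaplan-Meier, censored at transfer |
|---|---|---|---|
| Same constant hazard in both arms | 2% | about 1.95 | 1.98–2.01 |
| | 5% | about 1.86 | 1.98–2.01 |
| | 11% | 1.66–1.73 | 1.98–2.01 |
| Only infants who would stay over 14 days | 3% | loss of 0.2 or less | about 1.93 |
| | 8% | about 1.6 | about 1.85 |
| | 16–17% | 1.24–1.32 | about 1.70 |

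If both arms have the same SD, instead of the caffeine SD scaled by 12/14, the losses in the third column are somewhat smaller: about 1.9 days remain at 5% in the first pattern, and about 1.7 at 8% in the second.

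**4. Unequal transfer by arm** (lognormal, counting to transfer, placebo/caffeine transferred): 5%/2% gives 1.72; 10%/5% gives 1.50; 2%/5% gives 2.20; 5%/10% gives 2.32.

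**5. Power.** At 417 per arm, with lognormal stays and equal hazards, approximate power for the difference in medians is 0.86 to 0.88 with few or no transfers, 0.85 at 5%, 0.82 at 10% and 0.72 at 20% (simulation error about 0.02).

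**The case against.** The sponsor can make a fair case:

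- **Transfer may have been meant as leaving the network.** Read beside the exclusion, that is possible, but neither document says so. If it is the intention, a definition settles the network half of the point.
- **Stopping at transfer can be defended.** Discharge follows local criteria and a site-specific apnea countdown, blinded dosing depends on the study pharmacist, and the model adjusts for center. Days after a move may be off study drug and under other discharge habits. This stands as a cost of counting them, and it could dilute the effect. It does not justify analysing the transfer day as a discharge.
- **The plan has partial cover.** Survival models and a survival plot are listed, but not for the primary analysis. The 5% attrition allowance adds infants; it does not correct a shifted median.

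Stronger readings should be resisted:

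- A reader might infer that longer exposure to transfer makes even correct censoring invalid. It does not. A constant hazard that is independent of stay is ordinary independent censoring, and Kaplan-Meier recovers the full difference. Most of the loss in the table therefore comes from treating transfer as discharge. Only transfer that depends on expected stay leaves a residual, and the documents do not say who is transferred.
- A reader might infer that the bias is always toward zero. That holds only when transfer hazards are similar in the two arms.
- A reader might infer that transferred infants are often at a participating hospital, or that the date is easy to get. The documents say where subjects are enrolled, not where transfers go. That a receiving network hospital can supply the date is a reasonable inference, not a stated fact.

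**Conclusion.** The point holds. As written, an unqualified transfer ends the count for infants who are still hospitalized, including network moves that eligibility permits, and the primary model treats the transfer day as a finished stay.

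The size cannot be fixed from the documents. Under equal hazards and the assumed distributions, the loss is about 0.05 day at 2% transferred and 0.14 at 5%, reaching 0.27 to 0.34 at 11%. A censoring-aware analysis would recover it. What only the later discharge date can recover is the residual when transfer is tied to expected stay: about 0.07 day at 3%, 0.15 at 8% and 0.30 at 16–17%. With different transfer hazards by arm, either direction is possible. This should be corrected, but it does not undermine the trial if transfers are rare.

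**What to change.** In protocol Sections 1, 4.1 and 6.2 and SAP 3.2.1, 4.7 and 9.2:

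1. Define transfer, separating moves within the network from moves out of it.
2. Count days through a move between network hospitals to discharge home, up to 48 weeks post-menstrual age, with the receiving site supplying the date and the infant staying in follow-up.
3. After a move out of the network, obtain the discharge date from the parents or the receiving hospital where possible.
4. Where the date cannot be obtained, censor at transfer in a censoring-aware analysis instead of treating transfer as discharge. SAP 9.3 should name the method.
5. Report the number and type of transfers by arm, and keep the present rule as a sensitivity analysis.

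The cost is a wording amendment and one date per transferred infant, with no change to care. The drawback is that some counted days fall under another hospital's discharge practice and possibly off study drug, which may dilute the effect. That is consistent with the stated intention-to-treat analysis.
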